7.1.3. Study Duration

Patients will receive double-blind treatment for at least 48 weeks. Patients who have completed their 48-week, double-blind treatment period will continue double-blind treatment until all randomized patients have completed their 48-week treatment period and the database for that period is locked (approximately 3 years). An open-label extension study in which all patients receive OCA will be considered following review of blinded safety and PK data.

7.2. Number of Patients

Approximately 50 patients will be enrolled in this study.

7.3. Planned Dosing Regimen

All patients will initiate investigational product once weekly with OCA 5 mg or matching placebo (Table 2). Titration may be considered as early as the Week 12 Visit. Following visit procedures at Week 12, if the investigational product is tolerated and laboratory assessments do not indicate a safety concern, the patient may up-titrate to OCA 5 mg twice weekly and may start the higher dose regimen no earlier than 2 days after they took their last dose. Dosing will then occur at least 3 days apart. Every 6 weeks thereafter, based on tolerability assessments, patients can be considered for further up titration as described below (Table 2). At each titration visit, the patient may start the higher dose regimen no earlier than 2 days after the prior dose.

Patients may titrate to a maximum dose of OCA 10 mg twice weekly at least 3 days apart.

Table 2: Planned OCA or Matching Placebo Dosing Regimen

	Child-Pugh B and Child-Pugh C (Moderate and Severe Hepatic Impairment)	
	Treatment Group	
	OCA	Placebo
Starting Dose (Day 1)	5 mg once weekly	matching placebo once weekly
Titration 1 ^a	5 mg twice weekly ^b	matching placebo twice weekly ^b
Titration 2 ^a	10 mg twice weekly ^b	matching placebo twice weekly ^b

^a Planned titration regimen is shown; however, the titration of dose and/or frequency is dependent on patient tolerability.

^b Dosing per the twice weekly schedule must be at least 3 days apart.

7.4. Monitoring and Management of Potential Hepatic Injury and/or Disease Progression

Given the chronic nature of PBC, it is important to monitor for potential hepatic injury, disease progression and/or hepatic decompensation. Child-Pugh and MELD scores will be reviewed at each visit where labs are drawn (Table 1). In addition, adverse events, signs and symptoms of potential hepatic injury or decompensation, and laboratory values will also be reviewed at regular intervals as described in Section 7.1.2. Based on biochemical and clinical assessments, the investigational product may be interrupted or discontinued per criteria discussed in

Section 7.4.2 and [Section 7.4.3](#), and close monitoring procedures will be implemented (refer to [Section 7.6](#)).

7.4.1. Signs and Symptoms of Potential Hepatic Injury or Decompensation

Patients should be instructed to contact study personnel if they notice any of the following signs and symptoms or have healthcare interactions outside of the study setting

Signs and Symptoms of Hepatic Injury or Decompensation:

- Specific signs and symptoms of liver impairment: yellowing of the skin or the whites of eyes, pale-colored stools, urine color change from pale to deep amber [dark] (reflecting impaired bilirubin metabolism)
- More general signs and symptoms of ascites and encephalopathy: confusion, swelling of the legs or abdomen
- Non-specific signs and symptoms of impaired health: nausea, vomiting, abdominal pain, diarrhea, weight loss, fever and chills, worsening or new fatigue, weakness, loss of appetite
- Significant intercurrent illnesses such as gastroenteritis may exacerbate hepatic injury or decompensation (eg, established severe abdominal pain, vomiting, and diarrhea for more than 4 days) and should be an indication for prompt investigational product interruption and complete patient evaluation

Other Symptoms:

- Worsening of renal function or likely dehydration

Healthcare Provider (HCP) Interactions:

- Visits to primary HCP or referral to any specialist for any new symptoms (other than ongoing care for stable comorbidities)
- New medications or changes to current medications prescribed from HCP or any new over the counter medications or herbal supplements
- Laboratory procedures or assessments performed by an HCP

Signs and symptoms for potential hepatic injury or decompensation should be followed by (1) evaluation of liver biochemistry for suspected drug-induced liver injury (DILI) or potential hepatic decompensation (Section 7.4.2), (2) assessment of clinical events for potential hepatic decompensation (Section 7.4.3), (3) triggering of close monitoring or investigational product interruption/discontinuation per criteria ([Section 8.4](#)), (4) documentation in the AE eCRF or the SAE eCRFs ([Section 13.1](#)), and (5) contact with the Medical Monitor.

7.4.2. Liver Biochemistry Assessments for Potential Hepatic Injury or Hepatic Decompensation

[figure not shown]
Liver biochemistry will be assessed to evaluate biochemical triggers that will prompt an immediate reevaluation of patients for potential hepatic injury or hepatic decompensation. These assessments will be performed at:

- Each protocol-specified visit (Table 1)
- Unscheduled visits as needed in the event of signs or symptoms of suspected hepatic injury or decompensation or if laboratory alerts have been triggered

It is important that the laboratory assessments be completed as required and that the central laboratory be used for assessments whenever possible. In the event that a patient cannot return to the clinic for a scheduled or unscheduled visit, or there is an event that triggers a need for an immediate assessment, the use of a local lab is permissible at the discretion of the Investigator. In these cases, the Investigator will obtain the laboratory results and the laboratory normal ranges.

The process for assessing criteria is presented in Figure 2, and the specific threshold(s) for each laboratory analyte to trigger mandatory repeat testing and, potentially, a complete patient evaluation (depending on the repeat result) are summarized in Table 3.

Figure 2: DILI Management Algorithm

DILI = drug-induced liver injury; IP = Investigational Product

NOTE Other laboratory criteria include: ALT, AST, total bilirubin, INR, and electrolytes (sodium).

Table 3: Liver Laboratory Criteria for Monitoring of Suspected Hepatic Injury or Potential Hepatic Decompensation and Criteria for Interruption or Discontinuation of Investigational Product

Laboratory Criteria for Monitoring Suspected Hepatic Injury		
Laboratory Parameter	Action Taken	Rechallenging Criteria
Total Bilirubin		If a patient interrupts IP, they may be rechallenged after a minimum of 30 days if fully resolved OR stable and approved by the Medical Monitor and Investigator.
Baseline \leq ULN and \geq 3x baseline	Interrupt IP	
Baseline $>$ ULN and \geq 2x Baseline	Interrupt IP	
ALT or AST		
$>$ 3x baseline (and $>$ ULN)	Interrupt IP	
\geq 2x baseline	Repeat Test in 2 to 3 days, interrupt IP if still elevated	
Electrolytes^a		
Sodium $<$ 130 mEq/L	Repeat Test in 2 to 3 days, interrupt IP if still below limit	
Laboratory Criteria for Monitoring Potential Hepatic Decompensation (Absence of Clinical Symptoms)		
Total Bilirubin	Closely monitor until normalization or stabilization. If values continue to increase relative to the baseline value, interrupt IP.	The patient may be rechallenged after a minimum of 30 days if fully resolved OR stable and approved by the Medical Monitor and Investigator. If laboratory values do not normalize, IP should not be restarted.
Baseline \leq ULN and 1.5 mg/dL increase from baseline Baseline $>$ ULN and 1.0 mg/dL increase from baseline		
INR^b	Closely monitor until normalization or stabilization. If values continue to increase relative to the baseline value, interrupt IP.	The patient may be rechallenged after a minimum of 30 days if fully resolved OR stable and approved by the Medical Monitor and Investigator. If laboratory values do not normalize, IP should not be restarted.
$>$ 0.3 increase from baseline		
\geq 2.0 unless due to vitamin K deficiency	Discontinue IP permanently	Continue to return for scheduled study visits for safety follow up. Monitor closely for clinical outcomes per protocol.
Laboratory Criteria for Monitoring Potential Hepatic Decompensation in the Presence of Clinical Symptoms		
Total bilirubin thresholds defined in Part B OR an INR increase from baseline of \geq 1.5 are observed in the presence of clinical symptoms of cholestatic hepatitis or hepatic encephalopathy ^c	Discontinue IP permanently	Continue to return for scheduled study visits for safety follow up. Monitor closely for clinical outcomes per protocol.

IP = investigational product

^a Sodium will be measured as an assessment of liver failure (hyponatremia).

^b Does not apply in patients on anti-coagulants.

^c Symptoms of cholestatic hepatitis includes dark urine and jaundice. Symptoms of hepatic encephalopathy may include lack of awareness, shortened attention span, lethargy, gross disorientation, or coma (unresponsive to verbal or noxious stimuli).

It should be noted that it is difficult to recognize every potential marker of hepatic or renal deterioration. There is no substitute for good medical judgment. Investigators will be reminded to be cautious and mindful in their evaluation of patients' symptoms, signs, and laboratory results. However, for example, a single abnormal laboratory analyte result may be artefactual; accordingly, Investigators will be allowed to implement an alternate follow-up procedure if considered appropriate based on their medical judgement, but only after documented agreement with the Sponsor's Medical Monitor.

7.4.3. Clinical Criteria for Monitoring for Potential Hepatic Decompensation

Patients will be monitored for potential hepatic decompensation events throughout the study. Clinical criteria for monitoring these events and the interruption/discontinuation of investigational product is summarized in [Table 4](#).

Investigational product should be discontinued permanently if the patient received a liver transplant or experiences multi-organ failure as defined in Table 4, Part A. Patients should continue to return for scheduled study visits for safety follow-up.

Patients who experience other potential hepatic decompensation events defined in Table 4, Part B should be closely monitored until normalization or stabilization. Patients may be rechallenged after a minimum of 30 days if fully resolved OR stable and approved by the Medical Monitor and Investigator.

Table 4: Clinical Criteria for Monitoring Potential Hepatic Decompensation Events and Interruption / Discontinuation of Investigational Product

Hepatic Decompensation Events Requiring Mandatory Discontinuation of Investigational Product	
Decompensation Event	Action Taken / Rechallenging Criteria
Liver Transplant Multi-organ failure requiring hospitalization	Discontinue IP permanently and follow patients until normalization/stabilization. Continue to return for scheduled study visits for safety follow up.
Hepatic Decompensation Events Requiring Interruption of Investigational Product	

 1. Liver failure defined as worsening synthetic function that is persistently worse relative to baseline and/or progressive over time (see Table 3, Part B)^a 2. Variceal bleeding or recurrent variceal bleeding^b documented by endoscopy or accompanied by anemia or melena with a hemoglobin drop of ≥ 2 g/dL 3. Ascites^c including: 
 1. Worsening – requires increase in drug therapy or surgical intervention (paracentesis or shunt procedure) 2. Refractory ascites – unresponsive to medication; patient not candidate for transjugular intrahepatic portosystemic shunt (TIPS) or shunt; requires large volume paracentesis 3. Hyponatremia (≤ 125 mEq/L) secondary to ascites 1. Spontaneous Bacterial Peritonitis 2. Hepatic Encephalopathy, Grade ≥ 2 3. Any liver-related event requiring hospitalization and treatment (except multi-organ failure) 4. Hepatorenal syndrome Type 1 or Type 2 and acute kidney injury, hepatopulmonary syndrome, or portopulmonary syndrome 	
Closely monitor until normalization or stabilization.
 
The patient may be rechallenged after a minimum of 30 days if fully resolved OR stable and approved by the Medical Monitor and Investigator
 
IP should be re-initiated at a lower dose (or lower dose frequency) and titrated per Investigator discretion.

^a Patients experiencing INR ≥ 2.0 unless due to vitamin K deficiency should be discontinued from IP permanently without rechallenge and should to return for scheduled study visits for safety follow up.

^b Endoscopic confirmation of gastric or duodenal varices without evidence of bleeding should be closely monitored; investigational product may be interrupted at Investigator discretion

^c New onset ascites requiring treatment should be closely monitored; investigational product may be interrupted at Investigator discretion

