8.4. Dose Adjustment, Interruption, and Withdrawal from Investigational Product or Study

Investigational product may be temporarily decreased (eg, from 10 mg twice weekly to 5 mg twice weekly, or from 5 mg twice weekly to 5 mg once weekly) or temporarily or permanently stopped based on tolerability concerns. Investigational product may be resumed at the maintenance dose upon resolution of gastroenteritis or worsening renal function or dehydration if there is no evidence of liver injury. For rechallenge following all other dose interruptions (see Table 5), investigational product should be initiated at a lower dose and patients monitored more frequently with up-titration considered based on tolerability.

Adjustments, interruptions, discontinuation, and any rechallenge of investigational product should be implemented per the criteria outlined in Table 5. Patients that discontinue investigational product are expected to continue in the study (and follow the regular visit schedule, with the exception of PK sampling [trough PK may be required in the event of an AE consistent with hepatic injury or decompensation]) until the end of the study, but may withdraw consent at any time.

Table 5: Criteria for Dose Adjustment, Interruption, Discontinuation, and Rechallenge

DOSE ADJUSTMENT		
Criteria	Action Taken with IP	Adjustment
New Onset Severe Pruritus	Drug holiday or less frequent dosing	Return to original dose regimen if tolerated
DOSE INTERRUPTION		
Criteria	Action Taken with IP^a	Rechallenge^b
If liver biochemistries indicative of suspected hepatic injury are identified as exceeding upper threshold criteria and require immediate interruption (see Part A of Table 3) ^c	Interrupt immediately upon initial observation	Patient may be rechallenged after a minimum of 30 days if fully resolved OR stable and approved by the Medical Monitor and Investigator.
Other liver biochemistries indicative of suspected hepatic injury are outside upper threshold criteria upon repeat testing as defined in Part A of Table 3 ^d	Interrupt after confirmation by repeat testing	
Liver biochemistries indicative of potential hepatic decompensation in the absence of symptoms (see Part B of Table 3) ^e	Closely monitor until normalization or stabilization. If values continue to increase relative to the baseline value, interrupt	

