Clinical events indicative of hepatic decompensation (see Part B of Table 4)	Closely monitor until normalization or stabilization	The patient may be rechallenged after a minimum of 30 days if fully resolved OR stable and approved by the Medical Monitor and Investigator. IP should be re-initiated at a lower dose (or lower dose frequency) and titrated per Investigator discretion.
Gastroenteritis (established severe abdominal pain, vomiting, diarrhea for more than 4 days)	Interrupt	If no evidence of liver injury is detected, IP may be restarted at the same dose after resolution of intercurrent illness.
Evidence of worsening of renal function or dehydration	Interrupt	
DOSE DISCONTINUATION		
Criteria	Action Taken with IP	Rechallenge
If INR increases ≥ 2.0 in absence of clinical symptoms criteria (unless due to vitamin K deficiency) ^f	Discontinue / No Rechallenge	Discontinue IP permanently and continue to return for scheduled study visits for safety follow-up.
If total bilirubin thresholds (Part B of Table 3) are observed in the presence of clinical symptoms of cholestatic hepatitis or hepatic encephalopathy ^f		Continue to return for scheduled study visits for safety follow-up. Monitor closely for clinical outcomes according to protocol assessments.
Multi-Organ failure requiring hospitalization		
Liver transplantation		
Pregnancy		

Fully resolved = Return to baseline levels or return to within normal limits (WNL). IP = investigational product

^a If patient is unable to be evaluated promptly, study drug must be immediately interrupted.

^b Requires complete documentation of complete resolution or normal/baseline results based on laboratory parameters and symptoms.

^c Total bilirubin baseline \leq ULN and $\geq 3x$ baseline, baseline $>$ ULN and $\geq 2x$ baseline, ALT or AST $> 3x$ baseline (and $>$ ULN)

^d ALT or AST $\geq 2x$ baseline or electrolytes (sodium $<$ 130 mEq/L).

^e Total bilirubin baseline \leq ULN and 1.5 mg/dL increase from baseline OR baseline $>$ ULN and 1.0 mg/dL increase from baseline; INR $>$ 0.3 increase from baseline

^f If INR increases ≥ 2.0 in the absence of clinical symptoms or if or total bilirubin thresholds OR an INR increase from baseline of ≥ 1.5 are observed in the presence of clinical symptoms of cholestatic hepatitis or hepatic encephalopathy.

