9.7.7. Week 6 Procedures

Week 6 Visit should occur 3, 4, or 5 days after taking the Week 6 dose, eg, if the Week 6 dose is taken on a Sunday, the patient should come in for the Week 6 Visit within the following Wednesday and Friday ([Figure 3](#)).

- Verify that the patient has fasted for at least 8 hours.

- Record fasting status in the source and eCRF
- If the patient reports having eaten within 8 hours, document accordingly in the source and eCRF and remind the patient that fasting is required prior to all study visits, but water is permitted.
- Assess and record vital signs and weight (oral temperature, sitting heart rate, respiratory rate, and sitting blood pressure).
- Assess and record AEs.
- Review and record concomitant medications.
- Perform a physical examination.
- Review and record any non-study related medical or surgical treatment procedures and any medically relevant HCP or non-HCP related office visits that have occurred since the previous study visit.
- Perform assessments for calculation of CP Score ([Section 14.1.1](#)).
- Administer Quality of Life and Patient questionnaires (see [Section 13.2.7](#)).
- Assess investigational product compliance, perform investigational product accountability.
- Perform a urine-based β -hCG pregnancy test in females of childbearing potential.
- Obtain blood samples for
 - Serum chemistry, hematology, and coagulation
 - Bile Acids/C4/FGF-19
 - Fasting PK assessment
- Schedule the next visit, reiterate dosing instructions, and advise the patient:
 - NOT to take investigational product on the morning of the next visit, and
 - To bring the investigational product bottle(s); s/he will dose at the clinic (if this is in compliance with the established dosing frequency), and
 - To fast overnight (at least 8 hours) prior to the next visit. Fasting is required prior to all study visits, but water is permitted.

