12.1. Pharmacokinetic Blood Sampling

Serial and fasting PK assessments will be performed in all patients participating in the study.

[figure not shown]
At Day 1, and Weeks 6, 12, 18, 24, 30, 36, and 48, patients will provide fasted blood samples for measurement of OCA and its conjugates, glyco-OCA and tauro-OCA, and metabolite OCA glucuronide 30 minutes before administration of investigational product ([Table 8](#)). Patients will then receive a dose of investigational product with approximately 240 mL of water.

Week 6 Visit should occur 3, 4, or 5 days **after** the Week 6 dose (eg, if the Week 6 dose of investigational product is taken on a Sunday, the patient should come in for the Week 6 Visit between Wednesday and Friday [[Figure 3](#)]).

During the treatment period:

- Pharmacokinetic fasting samples will be obtained from all patients at Day 1, and Weeks 6, 12, 18, 24, 30, 36, and 48 prior to dose administration in accordance with [Figure 4](#).
- Serial PK assessments will be performed in all patients at Weeks 12, 18, 24, 30, and 48.

Figure 3: Week 6 Sampling Schedule

[figure not shown]

Week 6 Visit should be scheduled 3 to 5 days after the Week 6 OCA dose for collection of a single steady-state fasting PK sample

IP = investigational product; PK = pharmacokinetic

At Weeks 12, 18, 24, 30, and 48, serial PK blood samples will be obtained at 0.5, 0.75, 1, 1.5, 2, 2.5, 3, 4, 5, 6, 7, 8, 9, and 24 hours postdose (Figure 4) for all patients. The patient will be given the option to return to the clinic the following morning for the 24-hour postdose sample or samples can be obtained by a home health care designee. The home health care agency must be advised one week in advance of the appointment.

Figure 4: Pharmacokinetic Sampling Schedule

At meal timepoints, meals are consumed immediately after the collection of the PK sample

h = hour; IP = investigational product; PK = pharmacokinetic

Patients should not drink additional water for 1 hour after taking the dose of investigational product and will remain fasted until after the 1-hour sample is collected. A meal replacement drink will be provided following collection of the 1-, 4-, and 7-hour PK sample. The nutritional information of the meal replacement drink should be submitted to and approved by the Sponsor in advance. No other food or drink (water is permitted) will be allowed until after the 9-hour sample collection.

Table 8: Acceptable Windows for Pharmacokinetic Sample Collection

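### The protocol contradicts itself on rechallenge and on Week 6 dosing, and its action lines after hepatic decompensation omit the interruption that the table heading requires

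*Protocol*

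**What the plan says.** **Rechallenge.** In Table 3 (Section 7.4.2), the Part B cells for bilirubin and for INR allow rechallenge after at least 30 days if the abnormality has fully resolved or is stable, with approval by the Medical Monitor and the investigator. The same cells then add: "If laboratory values do not normalize, IP should not be restarted". Table 5 (Section 8.4) repeats the resolved-or-stable criterion. Footnote b on its Rechallenge column states: "Requires complete documentation of complete resolution or normal/baseline results based on laboratory parameters and symptoms".

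**Week 6 and Week 36.** Section 12.1 lists Day 1 and Weeks 6, 12, 18, 24, 30, 36 and 48 for a fasted sample 30 minutes before investigational product, and continues: "Patients will then receive a dose of investigational product with approximately 240 mL of water". Section 9.7.7 says: "Week 6 Visit should occur 3, 4, or 5 days after taking the Week 6 dose". Its procedure list contains a fasting PK sample and no clinic dose. Section 9.7.9 attaches clinic dosing to the serial sampling at Weeks 12 and 24, not to Week 36.

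**Interruption.** Part B of Table 4 is headed "Hepatic Decompensation Events Requiring Interruption of Investigational Product". The action cell opens "Closely monitor until normalization or stabilization", and the text of Section 7.4.3 says the same: "Patients who experience other potential hepatic decompensation events defined in Table 4, Part B should be closely monitored until normalization or stabilization". Table 5 places these events in its dose-interruption block, again with close monitoring as the action.

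**Restart level.** For interruptions other than gastroenteritis and worsening renal function or dehydration, Section 8.4 says "investigational product should be initiated at a lower dose and patients monitored more frequently". Table 4 also permits a lower frequency. The lowest regimen in Table 2 is 5 mg once weekly.

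**The concern.** These instructions decide whether a patient is on drug after a hepatic laboratory signal or a clinical decompensation, and how much drug is taken around Week 6. PK and safety are the two primary objectives (Section 6.1). The PK Population excludes patients with major deviations that could affect exposure (Section 15.1). If two instructions are live for the same situation, two sites can treat similar patients differently and both claim compliance, and it cannot be settled which patient deviated. The trial plans about 50 patients at about 50 sites, randomized 1:1. That is about 25 OCA patients, or 25/50 = 0.5 per site on average, so differences between sites in reading the text have little room to average out.

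**Working it through.** No stated figure has to be reproduced. The check sets current passages side by side, with simple dose arithmetic for Week 6.

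1. **Rechallenge.** Take a patient whose bilirubin or INR rose past a Table 3 Part B threshold, who interrupted, and whose value then settled above baseline without normalizing.
   - First sentence of the cell: stable, so eligible after 30 days with approval.
   - Next sentence of the same cell: not normalized, so barred.
   - Table 5 body: stable, so eligible. Table 5 footnote b: neither resolved nor at normal or baseline values, so barred.
   
   The same patient is both eligible and barred. The bar inside Table 3 appears only in the Part B rows. For Part A triggers the conflict arises only through Table 5 and its footnote b.

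2. **Week 6.** Inputs: starting regimen 5 mg once weekly (Table 2); first titration no earlier than Week 12 (Section 7.3); visit 3 to 5 days after the Week 6 dose (Sections 9.7.6, 9.7.7 and 12.1).
   - Planned intake in the 7 days from the Week 6 dose: 1 × 5 mg = 5 mg.
   - Intake if the dosing sentence in 12.1 is followed: 2 × 5 mg = 10 mg, with an interval of 3 to 5 days instead of 7.
   - Timing: 12 − 6 = 6 weeks before titration may first be considered. Table 2 reaches 10 mg per week only at Titration 1 (2 × 5 mg).
   - Over the first 12 weeks, assuming the other weekly doses are unchanged: 13 × 5 = 65 mg instead of 12 × 5 = 60 mg, and 5/60 = about 8% more.
   - Patients affected: at most 50/2 = about 25 on OCA, if every site followed 12.1 literally.
   
   The Week 6 sample is taken before any such dose under either reading, so that concentration is unaffected. Only later exposure differs.

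3. **Week 36.** Section 12.1 implies a dose after the sample and 9.7.9 lists none. Nothing fixes the visit between scheduled doses, so a dose that day could be the scheduled one. The texts differ, but no extra dose is shown.

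4. **Interruption.** The Table 4 heading and the Table 5 block say interruption. The action cells of both tables and the text of 7.4.3 say only close monitoring. Two comparisons show why the missing word matters. The neighbouring Table 5 rows for gastroenteritis and for renal worsening or dehydration state interruption outright. In Table 3 Part B, the same monitoring phrase is followed by interruption only if values keep rising, so there it means dosing continues meanwhile.

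5. **Restart level.** Each dose is one tablet, which must not be divided (Section 9.1), and Table 2 has no row below 5 mg once weekly. For a patient still on that regimen the lower restart has no defined step.

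The effect of items 1, 4 and 5 on exposure cannot be computed, because the protocol gives no expected rates for these events.

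**The case against.** The strongest reply concerns interruption. The Part B heading, the introduction to Table 4, the Table 5 block, the 30-day rechallenge rule and the re-initiation wording all presuppose that drug has stopped. Footnotes b and c of Table 4 make interruption discretionary only for lesser events, and Section 7.6 attaches close monitoring to interruption. This stands. A reader might infer that the protocol tells sites to keep dosing after variceal bleeding, peritonitis or encephalopathy. No line says so, and the defect is an action missing from the action lines.

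On Week 6, Section 12.1 itself places the visit 3 to 5 days after the dose and describes a single steady-state fasting sample. Clinic dosing for other visits is conditional on fitting the established frequency, and the Week 3 advice omits the clinic-dosing line used at Week 42. An extra dose in all 25 OCA patients is therefore a ceiling and not a forecast. The sentence in 12.1 still carries no such condition and names Week 6.

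On the lower restart dose, a reader might infer that every interruption before Week 12 is caught. It is not: gastroenteritis and worsening renal function or dehydration may resume at the same dose if there is no liver injury, and a pruritus holiday returns to the original regimen. Section 7.5 also lets investigators reduce dose or frequency. What remains is an undefined step.

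Medical Monitor approval gives central control over restarts after hepatic events. It limits variation but does not remove the rechallenge conflict, because the approver works from the same two criteria.

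**Conclusion.** The point holds in four parts of unequal weight.

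- **Direct contradictions:** the rechallenge criterion (Table 3 Part B internally; Table 5 against its footnote b) and the Week 6 dose (12.1 against the once-weekly regimen and 9.7.7).
- **Inconsistency by omission:** interruption after Table 4 Part B events.
- **Minor gap:** the lower restart dose, which matters only for patients on the starting regimen who interrupt for reasons other than gastroenteritis, renal worsening or dehydration, or pruritus.

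The only quantifiable effect is at Week 6: 10 mg instead of 5 mg in one 7-day interval for each patient dosed under the literal text of 12.1, with about 25 OCA patients as the upper bound. The exposure-safety relationship is an additional objective (Section 6.3), so it should not be counted among the primary ones. The primary PK and safety objectives are enough to require correction, because these instructions affect both patient safety and the question of who has an exposure-affecting deviation.

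**What to change.** Reconcile four sets of passages and use the same words in each place:

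1. Table 3 Part B, the Table 5 body and Table 5 footnote b: one rechallenge criterion.
2. Section 12.1 with 9.7.7 and 9.7.9: state for Week 6 and for Week 36 whether a clinic dose is given.
3. The Table 4 Part B heading with the actions in Table 4, Table 5 and Section 7.4.3.
4. The lower-dose restart wording in Section 8.4 and Table 4 with the regimens in Table 2, including what applies to a patient on the starting regimen.

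Which version is right in each case is a clinical decision for the sponsor, and this review takes no position on it. The cost is a clarifying amendment and a site notice, with no new visits, samples or patients. If patients have already been managed under the present text, the sponsor should also settle, before unblinding, how those cases are classed for the PK Population.
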